10.1.2 Expected AEs with Exercise Training and Testing (CPET)

Anticipated (expected) side-effects associated with a symptom-limited cardiopulmonary exercise test or exercise training include:

- Muscle soreness
- Joint pain
- Lower back pain
- Leg cramps

These anticipated side-effects associated with CPET will not be recorded as AEs as long as they are transient in nature.

Unanticipated but possible side-effects that are *rare, but serious* include:

- Cardiovascular: angina, AV blocks, bradycardia, edema, hypotension, palpitations, rebound hypertension, shock, syncope.
- Arrhythmias
- Myocardial ischemia
- Sudden cardiac death
- Cerebrovascular accident

These rare but serious AEs that may be related to CPET will be recorded as AEs or SAEs. The CPET may uncover previously unknown arrhythmias or other abnormal cardiac findings. These will be assessed for clinical significance by the cardiologist and/or Principal Investigator and will be recorded and graded as AEs if deemed to be clinically significant.

10.2 Serious Adverse Events

An AE is considered “serious” if in the opinion of the investigator it is one of the following outcomes:

- Fatal
- Life-threatening

- Constitutes a congenital anomaly or birth defect
- A medically significant condition (defined as an event that compromises subject safety or may require medical or surgical intervention to prevent one of the three outcomes above).
- Requires inpatient hospitalization or prolongation of existing hospitalization
- Results in persistent or significant incapacity or substantial disruption to conduct normal life functions.

10.2.1 Reporting of SAEs

Serious adverse events, whether or not considered drug related, should be reported to the lead site/sponsor (Duke) within 24 hours of becoming aware of the event, using the provided DCI SAE Report Form and the SAE Report Review Form (Site Assessment). These documents should be sent to:

The DCI Safety Desk – fax: [REDACTED]

If the safety desk cannot be reached within 24 hours, the Principal Investigator should be contacted: [name], [REDACTED]; email: [contact]

The initial report for each SAE or death should include at minimum the following information:

- Protocol # and title
- Patient initials, study identification number, sex, age
- Date the event occurred
- Description of the SAE
- Dose level and cycle number at the time the SAE occurred
- Description of the patient's condition
- Indication whether the patient remains on study
- Causality

Follow-up information including severity, action taken, concomitant medications, and outcome should be communicated to Duke as soon as possible.

Upon receipt of the Serious Adverse Event Reporting form by the DCI Safety Desk, the PI will be notified and be required to complete the PI assessment of the DCI Safety SAE Report Review Form. The DCI safety desk will, in turn, report the event to Astellas if felt to be at least possibly related to enzalutamide using the DCI SAE Report Form.

The SAE documentation, including the DCI SAE Report Form and available source records should be emailed or faxed to:

Astellas Pharma Global Development – United States
 Email: [REDACTED]
 Fax number: [REDACTED]

The following minimum information is required:

- Study number/IIT regulatory identifier
- Subject number, sex and age
- The date of report
- A description of the SAE (event, seriousness of the event)
- Causal relationship to the study drug

Follow-up information for the event should be sent within promptly (within 7 days) as necessary.

Follow-up information for the event should be sent within promptly (within 7 days) as necessary.

10.3 Procedure in Case of Pregnancy

The effect of enzalutamide in pregnant and lactating women is not known, and the exposure of a fetus or nursing infant is considered a potential risk. Enzalutamide can cause fetal harm when administered to a pregnant woman based on its mechanism of action. Subjects receiving enzalutamide are advised to use 2 acceptable methods of birth control (one of which must include a condom as a barrier method of contraception) starting at the time of screening for an enzalutamide study and continuing throughout the course of treatment and for at least three months after enzalutamide is discontinued.

If during the conduct of the clinical trial, a male subject impregnates his partner, the subject should report the pregnancy to the Investigator. With the permission of the pregnant partner, the Investigator should report the pregnancy to Medivation/Astellas as an SAE within 24 hours of awareness of the event. The expected date of delivery or expected date of the end of the pregnancy, last menstruation, estimated fertility date, pregnancy result and neonatal data etc., should be included in this information.

With the permission of the pregnant partner, the Investigator should report the outcome of the pregnancy (independent of outcome, e.g. full term delivery, pre-term delivery, spontaneous abortion, induced abortion, stillbirth, death of newborn, congenital anomaly [including anomaly in a miscarried fetus, etc.]) in accordance with the same reporting procedure as for SAEs. The date of outcome of the pregnancy, gestational age, date of birth and neonatal data etc., should be included in this information. Informed consent will need to be obtained from the pregnant partner to document her permission to disclose this information with Medivation/Astellas.

10.4 Safety Oversight Committee (SOC)

The Duke Cancer Institute SOC is responsible for annual data and safety monitoring of DUHS sponsor-investigator phase I and II, therapeutic interventional studies that do not have an independent Data Safety Monitoring Board (DSMB). The primary focus of the SOC is review of safety data, toxicities and new information that may affect subject safety or efficacy. Annual safety reviews includes but may not be limited to review of safety data, enrollment status, stopping rules if applicable, accrual, toxicities, reference literature, and interim analyses as provided by the sponsor-investigator. The SOC in concert with the DCI Monitoring Team (see **Section 11.1** for Monitoring Team description) oversees the conduct of DUHS cancer-related, sponsor-investigator therapeutic intervention and prevention intervention studies that do not have an external monitoring plan, ensuring subject safety and that the protocol is conducted, recorded and reported in accordance with the protocol, standard operating procedures (SOPs), Good Clinical Practice (GCP), and applicable regulatory requirements.

11 QUALITY CONTROL AND QUALITY ASSURANCE

11.1 Monitoring

The Duke Cancer Institute (DCI) Monitoring Team will conduct monitoring visits to ensure subject safety and to ensure that the protocol is conducted, recorded, and reported in accordance with the protocol, standard operating procedures, good clinical practice, and applicable regulatory requirements. As specified in the DCI Data and Safety Monitoring Plan, the DCI Monitoring Team will conduct routine monitoring after the third subject is enrolled, followed by annual monitoring of 1 – 3 subjects until the study is closed to enrollment and subjects are no longer receiving study interventions that are more than minimal risk.

Additional monitoring may be prompted by findings from monitoring visits, unexpected frequency of serious and/or unexpected toxicities, or other concerns and may be initiated upon request of DUHS and DCI leadership, the DCI Cancer Protocol Committee, Duke Clinical Trials Quality Assurance (CTQA), the Safety Oversight Committee (SOC), the Sponsor-Investigator, the site Principal Investigator, or the IRB. All study documents must be made available upon request to the DCI Monitoring Team and other authorized regulatory authorities, including but not limited to the National Institute of Health, National Cancer Institute, and the FDA. Every reasonable effort will be made to maintain confidentiality during study monitoring.

11.2 Data Management and Processing

11.2.1 Study Documentation

Study documentation includes but is not limited to source documents, case report forms, monitoring logs, appointment schedules, study team correspondence with sponsors or regulatory bodies/committees, and regulatory documents that can be found in the DCI-mandated “Regulatory Binder”, which includes but is not limited to signed protocol and amendments, approved and signed informed consent forms, FDA Form 1572, CAP and CLIA laboratory certifications, and clinical supplies receipts and distribution records.

Source documents are original records that contain source data, which is all information in original records of clinical findings, observations, or other activities in a clinical trial necessary for the reconstruction and evaluation of the trial. Source documents include but are not limited to hospital records, clinical and office charts, laboratory notes, memoranda, subjects' diaries or evaluation checklists, pharmacy dispensing records, recorded data from automated instruments, copies or transcriptions certified after verification as being accurate copies, microfiches, photographic negatives, microfilm or magnetic media, x-rays, subject files, and records kept at the pharmacy, at the laboratories and at medico-technical departments involved in the clinical trial. When possible, the original record should be retained as the source document. However, a photocopy is acceptable provided that it is a clear, legible, and an exact duplication of the original document.

11.2.2 Case Report Forms (CRFs)

The electronic CRF will be the primary data collection document for the study. The CRFs will be updated in a timely manner following acquisition of new source data. Only the research staff members listed on the delegation of authority log are permitted to make entries, changes, or corrections in the CRF.

An audit trail will be maintained automatically by the electronic CRF management system. All users of this system will complete user training, as required or appropriate per regulations.

11.2.3 Data Management Procedures and Data Verification

Completeness of entered data will be checked automatically by the eCRF system, and users will be alerted to the presence of data inconsistencies. Additionally, queries may be issued by the study data manager or project leader. Missing or implausible data will be queried for completion or correction (i.e. confirmation of data, correction of data, completion or confirmation that data is not available, etc.).

The database will be reviewed and discussed prior to database closure, and will be closed only after resolution of all remaining queries. An audit trail will be kept of all subsequent changes to the data.

11.2.4 Study Closure

Following completion of the studies, the PI will be responsible for ensuring the following activities:

- Data clarification and/or resolution
- Accounting, reconciliation, and destruction/return of used and unused study drugs
- Review of site study records for completeness
- Shipment of all remaining laboratory samples to the designated laboratories (i.e. BRPC at Duke)

12 STATISTICAL METHODS AND DATA ANALYSIS

All statistical analysis will be performed under the direction of the statistician designated in key personnel. Any data analysis carried out independently by the investigator must be approved by the statistician before publication or presentation.

12.1 Analysis Sets

The intent-to-treat (ITT) population will consist of all randomized patients. The modified intent-to-treat (ITT) population will consist of all randomized patients who have both a baseline and week 17 evaluation. In the ITT analyses and the modified ITT analyses patients will be analyzed according to the study arm to which they were randomized. The modified ITT population will be the primary analysis population.

The per-protocol population will consist of all randomized patients with both baseline and week 17 measurements for the primary endpoint and prior to any analysis: have been deemed compliant and properly evaluated for efficacy per investigator, satisfied all inclusion and exclusion criteria, and correctly assigned treatment.

The safety population will be all patients with at least one safety evaluation.

12.2 Subject Demographics and Other Baseline Characteristics

Demographics and baseline characteristics will be summarized for the ITT population. Mean, median, standard deviation, minimum, and maximum will be displayed by treatment arm for continuous variables. Categorical variables will be summarized by counts and percentages for each treatment arm.

12.3 Treatments

Compliance with supervised exercise training will be summarized as number and percent of exercise sessions attended.

Compliance with ENZ and ADT will be described, for each treatment arm, by the number and percent of intended doses taken. In addition, the number and percent of patients having delays or dose reductions will be displayed by treatment arm.

Numbers of patients discontinuing treatment and reasons for discontinuation will be displayed for each treatment arm. Numbers of patients failing to complete full follow-up (through week 36) and reasons for loss to follow-up will be displayed for each treatment arm.

12.4 Primary Objective

Refer to **Section 5** for the primary objective and endpoint. Briefly, the primary objective is to study the effect of supervised exercise training on cardiopulmonary function in men receiving the combination of enzalutamide (ENZ) and androgen deprivation therapy (ADT) for treatment of hormone-naïve prostate cancer.

12.4.1 Variable

The primary endpoint is the change in peak oxygen uptake ($\Delta\text{VO}_2\text{peak}$) from week 1 to week 17 in each group.

12.4.2 Statistical Hypothesis, Model, and Method of Analysis

The primary analysis will be comparison of the change in peak oxygen uptake ($\Delta\text{VO}_2\text{peak}$) from week 1 to week 17 between the usual care and exercise training groups, using a t-test. The primary analysis will be done for complete cases, (i.e. patients with VO_2peak measured at baseline and at week 17) in the ITT population.

Descriptive comparisons of $\Delta\text{VO}_2\text{peak}$ will be done:

- between baseline and end of week 4 to assess the effect of exercise (or usual care) alone,
- between end of week 4 and start of week 17 to assess the effect of exercise during ENZ + ADT treatment, and
- between the start of week 17 and the end of week 36 to assess whether there is a lasting effect of the supervised exercise regimen after it is discontinued.

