6 INVESTIGATIONAL PLAN

6.1 Study Design

This is a two-arm, non-blinded randomized (1:1) phase II trial to determine the efficacy on aerobic capacity of the combination of enzalutamide (ENZ) with androgen deprivation therapy (ADT) compared to the same regimen plus supervised exercise training (ENZ-ADT plus exercise training) in men with hormone-naïve prostate cancer. This study will be conducted at 2 centers: Duke Cancer Institute (DCI) and Memorial Sloan-Kettering Cancer Center (MSKCC). A total of 40 subjects will be enrolled. Subjects will be treated with enzalutamide plus ADT for 32 weeks. If randomized to the exercise arm, subjects will undergo supervised exercise training for 16 weeks.

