6.1.4 Randomization

Once the subject has been registered, completed screening, and found to eligible post-baseline testing, the study coordinator at Duke will request the subject's random assignment to one of the two treatment arms from the Medidata RAVE database.

For this pilot study, subjects will be randomly assigned with equal probability to either usual care or exercise training. A stratified block design will be used with randomization stratified by site only. Specifically, stratification will be: Duke versus MSKCC. This study is open label, meaning that neither subjects nor study personnel will be blinded to treatment assignment.

The site will then be notified by the RAVE database to which arm the subject has been assigned. For subjects who are not eligible and fail the screening process, no further action is necessary and no additional information will be collected. However, the number of screen failures and reason for screen failure will be collected at each site and tallied at the end of the study.

Case report forms will only be completed for those registered and randomized subjects, including those who do not receive treatment. However, subjects who do not receive the assigned treatment will be replaced and not counted toward the overall study sample size. Data limited to demographics will be collected for screen failures.

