Muscular Endurance of the upper and lower body will be assessed as the *number of repetitions to fatigue at 70% of the 1-RM*. The same exercises and methods will be used as in the 1-RM determination, detailed above. Subjects will continue until technique, tempo, volition or inability to complete two consecutive repetitions causes finality (per discretion of the exercise physiologist or trained designee).

Metabolic Control (protocol v1-v15 only)

Subjects will undergo sampling of fasting, pre-exercise, **plasma insulin** and **glucose** concentrations for calculation of **HOMA-IR**, as previously described.⁹⁷ **Glycosylated hemoglobin** (HgbA1c) will also be measured. These will be measured in a CLIA-certified clinical laboratory.

Body Composition

Body composition will be assessed by dual energy x-ray absorptiometry scan in the morning (after an overnight fast, if possible). Transverse scans from head to toe measured absorption of x-ray beams at two different energy levels allowing for a valid determination of lean body mass, fat mass and fat percentage.

Patient Reported Outcomes

Data on health related quality of life will be collected using the Functional Assessment of Cancer Therapy-Prostate (**FACT-P**) scale, which can be found in **Appendix C**.^{98,99} Data on subject-reported changes in fatigue will be collected using the Functional Assessment in Chronic Illness Therapy – Fatigue questionnaire (**FACIT-F**), which can be found in **Appendix B**. Data on leisure time exercise habits will be collected using the 4-item **Godin Leisure Time Exercise Questionnaire**, which can be found in **Appendix D**.¹⁰⁰

Food Frequency Questionnaire (FFQ)

A food frequency questionnaire (FFQ) developed by the Nutrition Assessment Shared Resource (NASR) of Fred Hutchinson Cancer Research Center (FHCRC) will be administered at the Week 1 and Week 17 time points to explore the collinearity of diet/exercise and to potentially correct for imbalances in the dietary intake between arms. Participants will be queried regarding their dietary intake over the last 1 month prior to completing the questionnaire.

Specifically, nutrient data will be collected using the Men's Nutritional Assessment (MNA). Nutrition Assessment uses the University of Minnesota Nutrition Data Systems for Research (NDSR) software for data entry and nutrient analysis via the FFQ. A sample booklet is provided at:

<http://sharedresources.fhcrc.org/sites/default/files/FFQ-MNA-Sample.pdf>

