12.5 Secondary and Exploratory Objectives

Refer to **Section 5** for the secondary objectives and endpoints. Secondary objectives are to compare effects on physical functioning / functional capacity, primary physiological determinants of VO_2peak , metabolic outcomes of interest, and subject-reported outcomes (PROs) of interest. The safety, feasibility, and acceptability of exercise training will also be evaluated.

Refer to **Section 5** for the exploratory objectives and endpoints. Exploratory objectives are to compare PSA response rates and describe metabolomics changes.

Secondary and exploratory endpoints are generally assessed at baseline, week 17, and at the end of week 36.

Descriptive comparisons of changes in secondary and exploratory endpoints will be done both:

- between baseline and the start of week 17 to assess the effect of exercise on changes due to ENZ + ADT, and
- between the start of week 17 and the end of week 36 to assess whether there is a lasting effect of the supervised exercise regimen after it is discontinued.

Continuous measures will generally be analyzed using a repeated measures model with the measure as the dependent variate and treatment arm and week of assessment as independent variates. Appropriate transformations will be used in cases where the measures the assumption of normally distributed errors would be violated.

Categorical measures will be analyzed using categorical data modeling techniques.

Whenever possible, transformation or categorization of secondary and exploratory measures will be done as reported in previously published studies in the field.

Eligibility rate is defined as the number of subjects found to be eligible for the study divided by the number approached for the study (i.e. screen fail rate). (Note: ineligible patients will not be randomized.) *Acceptance rate* is defined as the number of patients agreeing to participate divided by total number randomized.

Adherence rate is defined as the proportion of patients adhering to the exercise intervention (obtained from weekly exercise training attendance logs). *Attrition rate* is defined as the proportion of subjects who complete the 16 week exercise training program.

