12.6 Sample Size Calculation

The primary purpose of this study is to investigate to study the effect of supervised exercise training on cardiopulmonary function in men receiving the combination of enzalutamide (ENZ) and androgen deprivation therapy (ADT) for treatment of hormone-naïve prostate cancer.

The initial sample size calculations was based on the expected change in VO₂peak based on relevant prior reports or unpublished observations by the study team. Regarding the ENZ + ADT group, Segal et al.⁸⁰ reported that VO₂peak showed a mean decrease of 1.4 mL.kg.⁻¹min⁻¹ in 41 men initiating radiation with or without ADT for prostate cancer. During the same period, structured supervised resistance training completely abrogated the decline in VO₂peak observed in the usual care group. In unpublished data from our group among 50 men following prostatectomy for localized prostate cancer, mean VO₂peak was 29.5 mL.kg.⁻¹min⁻¹ (± 5.0 mL.kg.⁻¹min⁻¹). Following baseline assessments, subjects were randomly allocated to supervised aerobic training (n=25) or usual care (n=25) for 6 months. VO₂peak increased by 2.71 ± 3.5 mL.kg⁻¹.min⁻¹ in the exercise group and 0.6 ± 2.2 mL.kg⁻¹.min⁻¹ in the usual care group, resulting in a between group difference of +1.95 mL.kg⁻¹.min⁻¹ that favored the exercise training group (p=0.024).

Against this background, this protocol adopted the following assumptions: (1) a decline of 2.0 mL.kg⁻¹.min⁻¹ ENZ-ADT group from baseline to 16 weeks, and (2) an increase of 1.0 mL.kg⁻¹.min⁻¹ ENZ-ADT plus exercise training group from baseline to 16 weeks, for a between group delta of 3.0 mL.kg⁻¹.min⁻¹, favoring the ENZ-ADT plus exercise training group. A total of 56 subjects (n=28 / per group) provides 80% power to detect a mean 3.0 mL.kg⁻¹.min⁻¹ between group difference in VO₂peak from baseline to post-intervention, assuming a SD of 3.5 mL.kg⁻¹.min⁻¹ and a two-sided alpha of 0.05. These calculations assume a lost-to-follow-up rate of 15%, thus approximately 23 per group will provide evaluable data at 16 weeks post-randomization.

In November 2016, an interim analysis was performed due to the slow accrual and subjective feedback from subjects and exercise physiologists. That is, subjects in the exercise training group (Arm B) seemed to feel and perform better after the 16-week exercise training program compared with the usual care (Arm A) group at

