the same time point. A difference in the point estimates of $\Delta\text{VO}_2\text{peak}$ (week 1 to week 17) between groups was seen in the first 8 subjects who had completed testing for the primary endpoint of $\Delta\text{VO}_2\text{peak}$ at week 17 (N=4 each in the usual care and exercise training groups), suggesting less decline of VO_2peak in Arm B. Based on the interim analysis data, the study statisticians revised the sample size calculation.

We expect to use a one-sided t-test to check whether Arm B has a significant increase in VO_2peak from the baseline compared to Arm A. When each group has 20 evaluable subjects for significance level 0.10, we have 80% power to reject the null hypothesis that the two groups have the same change of VO_2peak given the effect size is 0.68 (the ratio of mean difference over common standard deviation). In case the test result is not significant, we will report the mean reduction descriptively with 95% confidence interval for this pilot study.

In summary, the revised sample size estimate is 40 total evaluable subjects, or 20 subjects in each arm.

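### The primary t-test on change in VO2peak leaves out baseline VO2peak and site. It is valid, but adjusting would gain about 1 to 3 power points using data already collected.

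*Combined protocol and SAP*

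**What the plan says.** Section 12.4.2 makes the primary analysis a comparison of the week 1 to week 17 change in VO2peak "between the usual care and exercise training groups, using a t-test", in complete cases. Section 12.6 repeats the choice when it revises the sample size: "We expect to use a one-sided t-test to check whether Arm B has a significant increase". It sizes the trial on that test: "When each group has 20 evaluable subjects for significance level 0.10, we have 80% power to reject the null hypothesis", at an effect size of 0.68.

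The design is a "two-arm, non-blinded randomized (1:1) phase II trial" (6.1). On allocation, 6.1.4 states: "A stratified block design will be used with randomization stratified by site only". The two strata are Duke and MSKCC.

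No other section puts baseline VO2peak or site into the primary analysis. The interpolation analysis (12.4.3) and the last-value-carried-forward analysis (12.5) change how missing values are handled, not the model. The repeated-measures model in 12.5 is for secondary and exploratory measures and lists only "treatment arm and week of assessment as independent variates". Section 9.12.3 collects diet data "to potentially correct for imbalances in the dietary intake between arms", but 12.4.2 has no covariate model in which any imbalance could be corrected.

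**The concern.** Subtracting baseline is not the same as adjusting for it. A change score assumes that a man who starts 1 unit fitter is, on average, exactly 1 unit fitter at week 17. If the true slope is below 1, less fit men tend to show the larger gains. A chance difference between arms at baseline then moves the estimated effect of exercise. Over all possible randomisations this averages to zero, so the test is not biased. It does add variance that could be removed.

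That matters more here than in a large trial. The target fell from 56 enrolled to 40 evaluable and the test is now one-sided at 0.10, so there is little precision to spare. The data needed are certain to exist: an acceptable baseline exercise test is an entry criterion (8.1), and everyone in the primary analysis has a baseline value and a site. The trial is open label and results by arm have already been seen in 8 men (12.6). Naming the covariates now also closes off a later choice between an adjusted and an unadjusted result.

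**Working it through.** **Inputs.** From the revised calculation in 12.6: effect size 0.68, 20 evaluable per arm, one-sided alpha 0.10, power 80%. From the earlier cohort in 12.6 ("In unpublished data from our group among 50 men following prostatectomy for localized prostate cancer"): baseline SD 5.0; SD of change 3.5 with exercise and 2.2 with usual care, pooled √((3.5² + 2.2²)/2) = 2.92. The initial sample size also used 3.5. The documents do not give the baseline to week-17 correlation, the week-17 SD or the site split. I assume equal SDs of 5.0 at both visits, then relax this in step 6.

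**1. The plan's own figure.** Noncentrality 0.68 × √(20/2) = 2.15 on 38 degrees of freedom, one-sided 0.10, gives 80.1%. The stated 80% reproduces. If 15% of 20 per arm are lost (the rate in the initial calculation), 17 remain and power is 75.0%.

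**2. Implied correlation.** With equal SDs, ρ = 1 − SDc²/(2 × 5.0²), where SDc is the SD of change.

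**3. Variance and power after adjustment.** The adjusted variance relative to the change score is (1 + ρ)/2 (gross). Allowing for estimation of k covariate slopes, multiply by 1 + k/(2n − 3 − k), with 2n − 2 − k degrees of freedom. At n = 20 the factor is 1 + 1/36 for baseline alone and 1 + 2/35 for baseline plus a site term that explains nothing.

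| SD of change | ρ | Gross ratio | Net, baseline | Power | Net, baseline + site | Power |
|---|---|---|---|---|---|---|
| 3.5 | 0.755 | 0.878 | 0.902 | 83.1% | 0.928 | 82.3% |
| 2.92 | 0.829 | 0.915 | 0.940 | 81.9% | 0.967 | 81.1% |
| 2.2 | 0.903 | 0.952 | 0.978 | 80.7% | 1.006 | 79.9% |

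At 17 per arm the model with both terms gives 76.9% (SD 3.5) and 75.7% (SD 2.92), against 75.0%.

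**4. Simulation.** The formula treats site as free to be imbalanced between arms, which stratified blocks largely prevent. I therefore simulated 20,000 trials per case with 20 per arm, site balanced across arms and no site effect.

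| SD of change | Site split within each arm | t-test | Baseline + site |
|---|---|---|---|
| 3.5 | 12/8 | 79.7% | 82.5% |
| 2.92 | 12/8 | 80.3% | 82.2% |
| 2.2 | 12/8 | 80.1% | 80.9% |
| 3.5 | 10/10 | 80.2% | 82.9% |
| 2.92 | 10/10 | 79.7% | 81.2% |

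Adding site to baseline changed power by about 0.1 point or less. In the 12/8 runs, type I error was 0.098 to 0.103 for the t-test and 0.098 to 0.102 for the full model, against 0.10. Both are valid.

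**5. Size of a chance imbalance.** The standard error of the baseline difference is 5.0 × √(2/20) = 1.58 mL/kg/min. The slope of change on baseline is ρ − 1, about −0.17 to −0.25. A one-standard-error imbalance shifts the unadjusted estimate by about 0.27 to 0.39. Two standard errors shift it by 0.54 to 0.77, or 27% to 33% of the difference the trial is powered for (0.68 × 2.92 = 1.99; 0.68 × 3.5 = 2.38).

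**6. Range if the SDs differ.** Take baseline SD 5.0, change SD 3.5 and week-17 SD s. The covariance is (25 + s² − 12.25)/2 and the gross ratio is (s² − cov²/25)/12.25.
- s = 4: covariance 14.375, ratio 0.631, power with both terms 90.7%.
- s = 6: covariance 24.375, ratio 0.999, power 78.4%.
- Neither term predicts change: also about 78.4%.

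**The case against.** The case against acting is fair in several respects. The t-test is valid, the sample size was computed for it, and the documents call this a pilot. The gain rests on a correlation they do not report, inferred from men who had prostatectomy and no enzalutamide plus ADT, followed for 6 months. At the usual-care change SD of 2.2 the formula shows a slight loss (79.9%), and across the assumptions tried the result runs from about 2 points lost to about 11 gained. Nothing in the documents shows that change in VO2peak differs by site. Protection against imbalance is also not a second benefit on top of precision: the variability is already in the t-test's standard error, and the change score removes most of a baseline difference, leaving 17% to 25%. The diet questionnaire does not promise a covariate in the primary model. Finally, the primary test would be changing after results by arm have been seen.

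Most of this stands as a limit on size. It does not defeat the point. The loss at SD 2.2 comes from charging site as a freely imbalanced covariate; with site balanced, the simulation shows a gain of 0.8 points. The downside is small, and the protection applies to the one randomisation this trial will have. The earlier look is a reason to settle and document the model before the final analysis.

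**Conclusion.** The point holds as a worthwhile improvement in precision. It is not an error in the plan: the unadjusted test keeps its level and its stated power. Assuming equal SDs at both visits and the earlier cohort's spreads, adjustment adds about 1 to 3 power points to 80.1%. Essentially all of that comes from baseline VO2peak. Any gain from site cannot be quantified from the documents; its inclusion rests on matching the analysis to the stratified randomisation. If site does predict change, a t-test that ignores the stratum tends to be conservative. Confidence in the size is moderate, because the correlation in men on enzalutamide plus ADT is unknown.

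**What to change.** In 12.4.2, replace the t-test with a linear model of week-17 VO2peak (or its change, which gives the same arm effect once baseline is in the model) on arm, baseline VO2peak and site (Duke or MSKCC). Keep the one-sided 0.10 test of the arm effect from 12.6, and report the adjusted difference with a two-sided 95% confidence interval. Keep the unadjusted t-test as a supportive analysis. Align the wording in 12.6, and record the change and its reason before the final analysis and without any further look at results by arm.

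The cost is one sentence in 12.4.2 and no new data. The model uses up to two degrees of freedom (38 to 36). A site term that predicts nothing costs up to about one power point by formula and about 0.1 in simulation with site balanced. If baseline predicts nothing either, power falls from 80.1% to about 78.4%. Because results by arm have been seen in 8 men, the amendment should say that the change rests on the design and not on those results.
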